4.1. Participants

We will recruit a minimum of 30 infants between 2 and 4 years old, identified as Late Talkers (children with a moderate or severe language delay) by Speech and Language therapists working for the Birmingham Community Healthcare NHS Foundation Trust.

4.1.1. Inclusion criteria

- Children (boys and girls) between 24 and 48 months.
- Children from Birmingham and its surrounding areas.
- Monolingual English native speakers
- Children with a moderate or severe language delay, as diagnosed by a Speech and Language Therapist of the Birmingham Community Healthcare NHS Foundation Trust.

4.1.2. Exclusion criteria

- Children with a developmental, physiological, neurological or cognitive disorder that could explain their language delay.
- Children with a mild language delay, as diagnosed by a Speech and Language Therapist of the Birmingham Community Healthcare NHS Foundation Trust.
- Children that speak or know another language different than English, either as first or additional language.

4.1.3. Participant identification and recruitment

We will recruit children via the Speech and Language Therapy Services from the Birmingham Community Healthcare NHS Foundation Trust. Parents/guardians of children that have been referred to these services are invited to attend an individual screening session. In this session, children are evaluated and divided into three categories: children with a mild language delay, children with a moderate delay, and children with a severe delay. Only children with a severe language delay are invited to take part in a subsequent intervention programme run by the NHS services, while it could currently take up to a year between the initial assessment and the start of the intervention. Parents/guardians of children with mild or moderate language delays are provided with guidance on how to support their child's language development and to contact the services again if the child seems to continue to lag behind their peers in their language development.

Parents/guardians of children that fulfil our inclusion exclusion criteria above (i.e. have either a moderate or severe language delay among other criteria) will be provided by the speech and language therapist with a brochure/leaflet (Appendix 1.1) about the present study at the end of the

initial assessment. The therapist will inform them that they can contact us in order to see whether the child might be able to participate in our study. In case of children with a diagnosis of severe language delay, the intervention will take place during the time that they wait for the start of their intervention conducted by the NHS services. They will be informed by the therapist and through the study brochure that their participation will not affect the services provided to them by the Birmingham Community Healthcare NHS Foundation Trust and that they will still receive an evaluation/intervention appointment with them in the future as planned.

The brochure (see Appendix 1.1) will contain information about the study, and the Chief Investigator/Researcher's contact details. If parents/guardians are interested, they can contact the Chief Investigator or researcher. If the children meet the inclusion and exclusion criteria and if capacity allows, they will be invited to take part in the present study at the Infant and Child Lab at the University of Birmingham.

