4.3.5. Higher-order generalization: At week 9, all infants will be assessed with four pairs of novel objects different to the ones used in previous sessions. The same procedure as the one for the first-order generalization will be followed and it will also last 8 minutes. This test will assess if infants have learned a general rule that one can extend novel labels based on shape similarities.

At the end of the study and independent of the type of intervention that the children took part in, parents/guardians will be asked about their thoughts about the development and implementation of the study, as well as about possible changes they made at home or any activities (such as music or dancing sessions) that their infants attended to while they were part of the study (see Appendix 1.6). Additionally, they will receive a Participant Debrief Sheet with more information about the specific intervention programme that their child received (see Appendix 1.7).

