4.4. Procedure of follow up study

A follow up study will be conducted one year after the start of the intervention programme in order to assess the long-term effects of the intervention in language and cognitive development. For this follow up study children's language, and cognitive abilities, will be assessed. The British Picture Vocabulary Scale (BPVS3) will be used to assess receptive language. In this test the child will listen to a word and will have to select from a set of pictures, the image that corresponds to that word. The Wechsler Preschool & Primary Scale of Intelligence - Fourth UK Edition (WPPSI-IV UK) will be used to assess infant's visual spatial skills and working memory. In this test, the child will be asked to recreate different figures using blocks and to view animal cards on a zoo layout for a specified time, remember where they are located, and then place each card in the previously viewed location.

5. Ethical considerations

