6.3.2 Primary outcome analysis

During weeks 8 and 9 of the study infants will be assessed with two forced choice tasks where they will have to extend object names to new exemplars based on visual commonalities. We will assess the statistical difference between the response pattern and chance (using t-tests). This will show whether infants have learned to extend object names by shape similarities. The factors that predict the number of noun extensions based on shape as well as vocabulary growth will be assessed using mixed effect model analyses. The most important factors tested in the models will be the number of words known before the intervention, the intervention type (shape training vs specific word training), attention measures (pre-test and attention during training), and sorting task measure. The outcome of these analyses will show whether the shape bias intervention has led to a larger vocabulary growth than the specific word intervention (as a control intervention). It will also assess the role of attention in word learning and whether only infants that pay attention to novel items

presented to them or infants that are sensitive to shape similarities between objects can acquire a shape bias. Only data of infants that complete the intervention will be analysed.

Regarding the follow up study, infants' vocabulary and cognitive abilities will be assessed. This with the aim of analysing if there are any long-term effects of each intervention and infants continue learning words and potentially "catching up", or if the intervention programmes are only beneficial while they are being implemented. The cognitive assessments will be used to assess whether the intervention has an effect on visual spatial skills and working memory. In both cases, it will be done by comparing the infants results to the standardized mean of UK infant population. Similarly, infant's result in the follow up language assessment will be compared to the standarized mean of UK infant population.

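### Severe-delay children who take up NHS therapy will normally have started it by the one-year follow-up, but the plan does not record it and reads one-year scores against UK norms as effects of the study programmes

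*Combined protocol and SAP*

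**What the plan says.** All references are to the combined protocol and SAP.

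- **Who is eligible (4.1.1):** "Children with a moderate or severe language delay, as diagnosed by a Speech and Language Therapist".
- **Who is offered NHS therapy (4.1.3):** "Only children with a severe language delay are invited to take part in a subsequent intervention programme run by the NHS services". Families of moderate-delay children receive guidance and may contact the service again.
- **The wait (4.1.3):** "it could currently take up to a year between the initial assessment and the start of the intervention".
- **Order of events (4.1.3):** for severe-delay children, "the intervention will take place during the time that they wait for the start of their intervention conducted by the NHS services". Taking part does not displace NHS care: "they will still receive an evaluation/intervention appointment with them in the future as planned".
- **Outside activities (4.3.5):** when the programme ends, parents are asked about changes at home and "any activities (such as music or dancing sessions) that their infants attended to while they were part of the study".
- **Follow-up (4.4):** "A follow up study will be conducted one year after the start of the intervention programme". The procedure lists the BPVS3 and the WPPSI-IV and nothing on therapy received in between. Sections 3.3 and 4.2 instead time follow-up from the end of the programme.
- **One-year analysis (6.3.2):** language and cognitive scores are compared with the UK standardised mean. The aim is to learn whether each programme has long-term effects or "if the intervention programmes are only beneficial while they are being implemented". Objective C (3.1) asks for something different, a comparison with the specific-word programme.

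**The concern.** For part of the sample, a second language programme is expected between the last study session and the one-year test. The plan has no way of knowing who received it, when it began or how much was given. A severe-delay child close to the norm at one year may be there because of the study programme, because of NHS therapy, or because some late talkers catch up unaided, as section 1.2 acknowledges. Comparing a group with a population norm cannot tell these apart, yet 6.3.2 uses that comparison to judge the lasting effect of each programme. Long-term effect is one of the three primary objectives. The end-of-programme results (Objectives A and B) are not affected, because the plan has severe-delay children still waiting at that point.

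**Working it through.** The plan states no figure to reproduce on this point. The check is a timeline in months from the NHS initial assessment.

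**Inputs**
- W, the wait until NHS therapy starts: at most 12 (4.1.3). The typical wait is not given.
- L, the lag from that assessment to study session 1: at least 0, because recruitment begins at the end of the assessment (4.1.3). It is not given, so it is varied.
- Programme length: 9 weekly sessions (4.2), so 8 weeks from first to last, and 8 × 7 / 30.44 = 1.84 months.

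**Time of follow-up**
- Timed from programme start (4.4): L + 12.
- Timed from programme end (3.3, 4.2): L + 1.84 + 12 = L + 13.84.

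**Shortest time since NHS therapy began, with W = 12**

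| L | Timed from start: L + 12 − 12 | Timed from end: L + 13.84 − 12 |
|---|---|---|
| 0 | 0.0 | 1.8 |
| 1 | 1.0 | 2.8 |
| 3 | 3.0 | 4.8 |
| 6 | 6.0 | 7.8 |

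The value is never negative. The one tie (0.0) needs the full 12-month wait, no lag, and timing from programme start.

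**Longest time.** NHS therapy follows the study programme, so it starts no earlier than L + 1.84. The longest time is then 12 − 1.84 = 10.2 months (timed from start) or 13.84 − 1.84 = 12 months (timed from end). The stated facts thus allow about 0 to 10 months, or about 2 to 12 months. This is time since therapy started, not amount of therapy: the length and intensity of the NHS programme are not given.

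**Can the recorded data show it?** The questionnaire on outside activities is completed at the end of the programme, before NHS therapy begins in the planned order. The session 1 questionnaire (4.3.1) is earlier still. Section 4.4 adds nothing. Neither severity nor NHS therapy is among the baseline variables in 6.3.1 or the model factors named in 6.3.2.

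**Size against norms, on assumed values.** If a share s of a group is severe and takes up therapy, and therapy has moved those children by e SD at follow-up, the group mean moves by s × e.
- Low: 0.25 × 0.2 = 0.05 SD.
- Middle: 0.5 × 0.5 = 0.25 SD.
- High: 0.75 × 0.8 = 0.60 SD.

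The documents give neither s nor e. If therapy has only just begun, e is near zero.

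**The case against.** **NHS therapy is not the only obstacle to attribution.** Because some late talkers catch up unaided, a one-group comparison with norms could not credit a programme even if nobody had NHS therapy. This stands. It means that recording therapy is not enough and that the one-year comparison itself has to change.

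**Between randomised arms there is no bias.** Therapy starts after allocation and is available as planned in both arms, so the arm difference validly estimates allocation plus usual care. This also stands. A reader might infer that later therapy confounds the comparison, or that uneven uptake in arms of 12 to 15 could pass for an effect. Chance imbalance is ordinary sampling error, already carried in the standard error.

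**The direction of any change is not fixed.** A reader might also infer that therapy must shrink the arm difference, so that a null result would be misleading. The documents do not support that. If therapy adds equally in both arms, nothing is lost; if shape-trained children gain more from it, the difference grows. No dilution percentage can be derived.

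**Only the start is bounded.** The year is the service's current upper limit, not a guarantee, and the promised appointment may be for evaluation rather than therapy. It would be too strong to say that the whole NHS programme falls before follow-up, or that every severe-delay child will have had it. This limits the claim without removing it.

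**Severity is known at screening.** Since it decides eligibility, imbalance in who is invited to NHS therapy could be checked by arm if severity is carried into the dataset. Uptake, start date and amount could not.

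**The sentence in 6.3.2 states an aim.** It sets out two possibilities and is not a decision rule for a null result. That is fair, but the comparison offered cannot distinguish the two.

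**Conclusion.** The point holds as a matter of attribution and missing data. On the stated wait, severe-delay children who take up NHS therapy will normally have started it by follow-up, under either timing rule. The amount received is unknown and would remain unknown. The planned norm comparison cannot separate the programme from NHS therapy or natural catch-up. The part wrongly credited could be 0.05 to 0.60 SD on the assumed values, and close to nothing if therapy has barely begun.

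This rests on the current maximum wait of a year, on the order of events in 4.1.3, and on Appendices 1.5 and 1.6 being used only when sections 4.3.1 and 4.3.5 say they are. It is not a claim that the randomised comparison is biased. It is a worthwhile, low-cost improvement to the one-year part of the study.

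**What to change.** - **Section 4.4:** at the one-year visit, ask all families whether speech and language therapy was received since week 9, when it started and how many sessions were attended. Include moderate-delay families, who may have gone back to the service. Tabulate by arm and severity.
- **Section 6.3.2, analysis:** make the randomised arm difference that Objective C asks for the primary one-year analysis, without conditioning on therapy received. Keep the comparison with UK norms as descriptive only.
- **Section 6.3.2, interpretation:** state that one-year results are the effect of allocation on top of any later NHS therapy.
- **Moderate-delay children alone:** at most exploratory. With 24 to 30 children and an assumed severe share of 0.3 to 0.7, between 24 × 0.3 / 2 = 3.6 and 30 × 0.7 / 2 = 10.5 per arm remain, roughly 4 to 10. At an assumed standardised difference of 0.5, power is about 9% to 19%. The subgroup is also not free of re-referral.
- **Follow-up timing:** reconcile 4.4 (from programme start) with 3.3 and 4.2 (from programme end).

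The cost is a few parent questions at an existing visit and one table. The arm comparison uses scores already planned. The therapy data will rest on parents' recall.

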4.1.4. Consent

Parents/guardians will consent their willingness to take part in the study on behalf of their children. They will receive a detailed information sheet (see Appendix 1.2) and a verbal summary of the study by the researcher at the beginning of the initial session of the intervention programme. After this summary and before commencing the first training/testing, they will be asked to sign a consent form (see Appendix 1.3). This consent form states the activities the child will be introduced to and the duration. It emphasizes that participation is completely voluntary, that the parent/guardian can withdraw his/her child from the study at any time up to 1 month after the final session of the intervention programme and without giving any reason, and that this will not have any impact on any services provided by the Birmingham Community Healthcare NHS Foundation Trust in the future. Parents will also be informed that a follow up study will be conducted and will be asked to provide a separate signature if they agree to be contacted in the future to follow up on the progress of their child or not. With regards to the infants, a simple explanation (age appropriate) of the tasks will be provided to them. Afterwards, infants will be asked if they want to "play" with the researcher.

4.1.5. Withdrawing criteria

Parents/guardians can fully withdraw their infants from the study at any stage and up to 1 month after the final session of the intervention programme without the need of providing any explanation. If this happens, all existing paper forms and electronic data related to the infants will be destroyed and their details in the participant database will be deleted. They will therefore not be contacted for any follow-up study. Parents/guardian can also decide not to take part in the follow-up study, either

by not signing the agreement for the follow-up contact on the initial consent form or by informing the researcher when being contacted to make arrangements for the follow-up testing. As with the intervention programme, parents/guardians can withdraw their children from the follow-up study at any time up to 1 month after the completion of the follow-up test. Parents will be informed that their decision to withdraw from the study will not affect any services provided to them by the Birmingham Community Healthcare NHS Foundation Trust.

4.2. Study design

Infants will be randomly allocated to one of two groups: shape training group or specific word training group. Over a series of 9 weekly sessions, all infants will be assessed on different tasks that can be divided into 5 stages: Vocabulary and developmental assessments, initial cognitive assessments, training sessions, first-order generalization test, higher-order generalization test. Depending on the group that the children will be in, they will receive either a shape training or a specific word training. Other assessments (initial assessments, cognitive assessments, first-order generalization test and higher-order generalization test) will be identical across the groups. Additionally, a follow up study will be conducted after one year of completion of the intervention programme. A table describing the intervention procedure is provided in Figure 1. Details of the tasks are given below.

[figure not shown]

Figure 1. Timeline of intervention programmes.

4.3. Tests and procedure of intervention programme

4.3.1. Vocabulary and developmental assessments. At session 1, parents/guardians will fill in a socioeconomic and general development questionnaire (see Appendix 1.5). The

information provided in this questionnaire will double-check the inclusion/exclusion criteria. It will also be used to check whether the intervention was only successful in a sub-group of the infants (e.g. those without a family history of language problems). In the first and last session, parents/guardians will also be asked to fill in the UK-CDI Words and Gestures questionnaire, a vocabulary checklist of words and phrases that infants might know and use (Alcock, Meints, & Rowland, 2017; see Appendix 1.4). This will allow us to compare language development during the intervention programme between the two intervention groups.

4.3.2. Initial cognitive assessments: The initial cognitive assessments will be presented during the first two sessions. During week 1, infants will be assessed with a shape sorting task and an attention task. The sorting task will last no more than 5 minutes and will be used to assess if before the training programme, infants are sensitive to the shape of objects and can group objects by shape. Infants will be presented with 16 novel objects differing in shape, colour and texture and asked to sort them into groups. How to sort (namely by shape) will be shown to them with the means of examples. The attention task will last 3 minutes and will assess infants' joint and sustained attention. This will be achieved by monitoring their eye movements during the presentation of five short video clips (35 seconds each) of a person looking at and moving unusual novel objects. For this task, participants will sit on their parent/guardian's lap in front of a computer screen. Eye movement will be monitored with a remote eye tracker (see Figure 2). The parent will wear blacked-out glasses so that their behaviour cannot affect the infants' eye gazes.

At week 2, infants' visual spatial abilities and working memory will be assessed using the Wechsler Preschool & Primary Scale of Intelligence - Fourth UK Edition (WPPSI-IV UK). This test will last about 20 minutes and will be used to rule out any potential cognitive delay.

Figure 2. Attention task. Infants will watch five short videos and eye movements will be monitored with a remote eye tracker.

4.3.3. Training sessions

4.3.3.1. Shape training: During the first seven weeks, infants will be presented with four novel words paired with four novel sets of objects (total duration 15 minutes). Each set will consist of two exemplars with the same shape but with different colours and textures. Each set will be presented with sentences such as “*Look! It is a kiv. Do you want to play with the kiv?, Let’s play with the kiv*”. Half way through the presentation of the exemplars, the researcher will bring out a third contrasting object. This contrasting object will be presented with the sentence “*Oh no, this is not a kiv*” and will be taken away immediately. The other three sets of novel exemplars will be presented in the same manner.

4.3.3.2. ‘Specific word’ training: This training will resemble a typical word learning intervention. During the first seven weeks infants will be introduced to 28 real common objects and their names (e.g. biscuit, trousers, slide), randomly divided into 7 sets of four words. During each session, infants will be presented with one of the sets and each session will have a total duration of 15 minutes. The target words have been selected from the Wordbank database, an open database that lists the proportion of children that know a specific word at a specific age. Twenty-eight words that 80% of the total child population at 25 months know were randomly selected as target words. Each session will consist of a 15 min play session in which each object name will be presented at least 10 times and each object name will be mentioned at least 10 times. Additionally, techniques such as focused stimulation and modelling target words, which have proved to be useful for word learning, will be used.

4.3.4. First-order generalization: At week 8 infants in both groups will be assessed as to whether they have learned that objects that have the same shape share the same name. They will be presented with each exemplar used during the training sessions accompanied by three novel toys. These three objects will share only one visual property with the training objects (colour, shape or texture). The three objects will be placed on a table and the researcher will say “*This is a kiv, Can you show me the other kiv?*” while he/she shows the infant one of the exemplars used during the 7 training weeks. All infants will be tested on each trained object with the same procedure. This test will last 8 minutes.

4.3.5. Higher-order generalization: At week 9, all infants will be assessed with four pairs of novel objects different to the ones used in previous sessions. The same procedure as the one for the first-order generalization will be followed and it will also last 8 minutes. This test will assess if infants have learned a general rule that one can extend novel labels based on shape similarities.

At the end of the study and independent of the type of intervention that the children took part in, parents/guardians will be asked about their thoughts about the development and implementation of the study, as well as about possible changes they made at home or any activities (such as music or dancing sessions) that their infants attended to while they were part of the study (see Appendix 1.6). Additionally, they will receive a Participant Debrief Sheet with more information about the specific intervention programme that their child received (see Appendix 1.7).

